4.11 SUBJECT COMPENSATION

We will offer participants in the semi-structured interviews monetary compensation of \$100 with a Clincard gift card.

5. ASSESSMENTS

5.1 RISK BENEFIT

The risk/benefit ratio of this study is very favorable. The study team will take necessary steps to maintain confidentiality and privacy throughout the study period.

The potential risks associated with this study are minimal. Breach of data is a potential risk that will be mitigated by using HIPAA compliant and secure data platforms as described. There are also potential emotional risks to patients if they misunderstand the role of palliative care. Our research coordinator will be trained in helping patients and their caregivers understand the supportive role of palliative care.

There may be some emotional discomfort or distress with doing patient-reported surveys. If this occurs, subjects will have the option to stop the phone call and questionnaire, and we will also provide support resources to help cope with this afterwards including referral to our internal psychology team or state-funded mental health support crisis [contact]).

6. STATISTICAL CONSIDERATIONS AND ANALYSIS PLAN

6.1 GENERALIZED CONSIDERATIONS

Our study setting is a large community-based oncology network. This population is similar to many other community oncology practices in that it is not affiliated with a large hospital or health system, and thus the major source of palliative care is in the outpatient setting. However, Tennessee Oncology has a robust outpatient and telemedicine palliative care infrastructure consisting of 2.5 FTE physicians and 8.0 FTE advance practice providers. Our study findings may be challenging to generalize to oncology practices with limited access to outpatient specialty palliative care. However, within the next 5-10 years, most community oncology practices will have access to ambulatory or telemedicine outpatient palliative care. Furthermore, our algorithm-based approach accounts for limited palliative care capacity by customizing thresholds; thus, it is more flexible than previously-used rules-based triggers.

We expect to generate results and manuscripts within 2 years due to quick enrollment and the presence of an existing and accepted risk score, which obviates the need to create another algorithm. If necessary, we will submit an amended version requirement by spacing out PI, co-investigator, and research coordinator effort and enrollment over a three-year period and by using a higher risk score threshold to control high-risk patient enrollment.

Due to payer considerations with the COVID-19 pandemic, telemedicine palliative care has been reimbursed at ambulatory rates; thus, 40% of palliative care visits at Tennessee Oncology are currently via telemedicine. Reimbursement landscape changes may impact palliative care access, although this would occur in both the control and intervention arms and should not compromise the intervention effect.

6.2 PATIENT & FAMILY PERCEPTIONS

The phrase “palliative care” is often stigmatized to the point where patients and their caregivers sometimes are fearful of this clinical service, worried that it means cancer-directed treatment is no longer effective. Our coordinator will educate and explain the focus on quality of life regardless of their treatment plan or outcome. Furthermore, we will make every effort to schedule in-person or telemedicine visits to minimize patient and caregiver burden

6.3 RISK SCORE

To identify patients who may benefit most from early outpatient palliative care, we use a rules-based algorithm based on 14 NCCN-endorsed criteria for palliative care referral. This stands in contrast to previous randomized trials that have randomized patients to palliative care at the point of diagnosis. Compared to such trials, our approach may identify patients relatively late and does not pre-specify the frequency of palliative care appointments. However, this approach is generalizable to other systems that collect similar data, since outpatient specialty palliative care at the point of diagnosis is often infeasible due to lack of palliative care capacity. Furthermore, our algorithm still identifies patients well before the immediate end-of-life period, and thus is expected to increase referrals among many eligible patients. The risk algorithm also ensures that the highest risk patients get seen earlier and in a more-timely fashion.

6.4 ANALYSIS MEASURES

The primary study endpoint is completion of a palliative care visit within 3 months of enrollment *among high-risk patients*. The secondary outcome is completion of palliative care visits among non-high-risk patients.

We will also assess on an exploratory basis the impact on acute care utilization including emergency room visits and hospitalizations within participating hospitals in the state of Tennessee; completed palliative care visits among all patients at Tennessee Oncology; number of opioid prescriptions; aggressive end-of-life care (no hospice referral or enrollment prior to death, hospice enrollment<3 days before death, location of death and/or chemotherapy receipt within 14 days of death) and patient-reported measures including depression, pain, quality of life measured by FACIT-PAL 14, and the heard and understood measure. All exploratory outcomes will be measured by descriptive statistics.

Patients will be followed for exploratory outcomes for six months or death.

The semi-structured interviews will be transcribed and uploaded to Atlas.ti, a data management software. We will inductively develop a codebook following the initial interviews based on the structure of the interview guide. One of two reviewers will code each transcript, and approximately 20-

25% of total transcripts will be coded by both reviewers to establish inter-rater reliability. The adequacy of the codebook will be periodically assessed by the reviewers in partnership with the research team and modifications will be made as their understanding of the data and emergent themes evolves over time. The reviewers will meet regularly to discuss discrepancies and update the code book as needed, with record keeping adequate to track changes to the code book and the rationale. Kappa statistics will be generated to estimate inter-rater reliability. Coding will then be reviewed to summarize key themes, and representative quotes will be selected to illustrate those themes.

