3.3 SECONDARY OUTCOMES

- Completed palliative care visit among non-high risk patients with stage III and IV lung and non-colorectal GI malignancies.

We will also assess on an exploratory basis the impact on acute care utilization including emergency room visits and hospitalizations within participating hospitals in the state of Tennessee; completed palliative care visits among all patients at Tennessee Oncology, number of opioid prescriptions, aggressive end-of-life care (no hospice referral or enrollment prior to death, hospice enrollment<3 days before death, location of death and/or chemotherapy receipt within 14 days of death); and patient-reported measures such as depression and pain. We will also assess on an exploratory basis the quality of life of patients in the intervention group and control group through the FACIT-PAL 14, and “Heard & Understood” instrument before the palliative care visit, and after the visit at 1-month, 3-month and 6-month intervals (see **Exhibit 4**).

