4. STUDY DESIGN

4.1 RANDOMIZATION & RECRUITMENT

This 2-arm randomized trial (six-month enrollment; six-month follow-up) will enroll approximately 400 patients with advanced lung and gastrointestinal malignancies and 40 clinicians to assess response to behavioral nudges to refer to palliative care at up to 17 practices within Tennessee Oncology, a US community oncology network. All practices have access to palliative care and will be randomized to usual care vs. intervention. The outcome is completion of a palliative care visit within 3 months among high-risk patients.

We will randomize practices into two arms using permuted block randomization to balance practice size, baseline palliative care referral rate (see **Exhibit 1**). The Principal Investigator ([name]) and primary statistical analyst will be blinded to arm assignment.

This 2-arm randomized trial (six-month enrollment, six-month follow-up) is taking place at Tennessee Oncology. Tennessee Oncology, one of the nation’s largest, community-based cancer care specialists, is home to one of the leading clinical trial networks in the country.

Eligible clinicians will receive notification about the trial via email and in-person presentations. High-risk patients for the intervention will be identified from weekly runs of the risk score algorithm, in coordination with [name], Tennessee Oncology Care Data Systems Manager.

For the semi-structured interviews, the research team at Tennessee Oncology will create a list of potential clinicians. We will initially contact potential participants via email (see **Exhibit 6**), and if we do not get enough participation, coordinator and site investigator will do in-person recruitment with clinicians. For participants that agree to do the interview, clinical research coordinator will create a research ID for each participant that only key members of research team will have access to. Coordinator will subsequently create a de-identified dashboard to track mode of interview (in-person, virtual, telephone), length of interview, participant characteristics (gender, years in practice, palliative care v oncology, physician v nurse practitioner), and to store audio files, transcripts, and analysis documents. To ensure an adequate number of perspectives on the trial, we will use purposive

sampling to sample clinicians who performed at or above vs. below the median response to the intervention.

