4.4 TARGET POPULATION

Approximately 400 patients with advanced malignancies and up to 80 clinicians to assess response to behavioral nudges to refer to palliative care at up to 17 practices within Tennessee Oncology. The split will be into two arms: approximately 200 intervention, 200 control, and up to 40 clinicians in each arm. Clinicians will be clustered to a single practice for the intervention and analysis in order to avoid contamination of intervention effect into the usual care arm.

Our target population for the semi-structured interviews includes clinicians at Tennessee Oncology that were included either in the intervention group as oncology providers, and palliative care clinicians at Tennessee Oncology that saw patients referred through our intervention.

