8.3 INFORMED CONSENT

For administering quality of life and communication questionnaires, we request a verbal consent process. This is requested since our intervention will be being conducted via telephone and with the large geographic distribution of our practice (over 130 miles between clinics), it would not be feasible to obtain written consent for the questionnaire component of the study for patients. An information form will be read to the patient and mailed to them if they consent to completing the questionnaire via telephone.

For the intervention itself, a waiver of informed consent is requested. This is a health system initiative that will be implemented. The study is to evaluate that initiative. Therefore, physicians and their patients will not be consented as this is the standard of practice per the health system initiative. Without a waiver of the consent, the initiative would still be implemented by the health system, but the study would be infeasible. There are several additional reasons why we feel a waiver of consent should be granted. First, it is not feasible to consent every physician and as mentioned this initiative would occur with or without the study of it. Second, if members of the control group were consented, this alone could change their behavior. This could potentially disrupt the design of the study and making interpretation of the findings challenging. Third, physicians are not being forced to refer patients to palliative care. This intervention decreases the cognitive burden of remembering which patients are appropriate and would benefit from palliative care. The oncologist always retains control of the referral by being able to "opt-out" and cancel the referral on a case by case basis. This intervention is working towards better implementation of what is considered standard of care for patients with advanced care.

Verbal consent will be obtained from each clinician who participates in the semi-structured interviews (see **Exhibit 7**). Written consent is not necessary for this part of the project because clinicians will not be required to participate and can opt out at any point. No patient identifying information will be provided to clinicians.

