Bone Metastases in Diagnosis List or Charge	If exists	1	1
Secondary malignant neoplasm of brain	If exists	1	1
COPD in diagnosis list or charge	If exists	1	1
CHF in diagnosis list or charge	If exists	1	1
Dementia in Diagnosis List or Charge	If exists	1	1
Liver Cirrhosis in diagnosis list or charge	If exists	1	1
Stroke in diagnosis list or charge	If exists	1	1
Spinal cord compression in Diagnosis list or charge	If exists	1	1
Most recent NCCN Distress Score	≥ 8	1	1
Most recent ECOG Performance Score	≥ 2	1	1
Most recent PHQ-2 Score	≥ 3	1	1
Number of ED visits in prior 3 months	Each ED visit receives 2 points	1	2
Number of Inpatient stays in prior 3 months	Each Inpatient stay receives 2 points	1	2
Low Age	<40	1	1
High Age	≥ 70	1	1

Total Risk Score	Interpretation	Time to Palliative Care Visit
>1 Stage IV, >2 Stage III	High Risk	2 weeks
<1 Stage IV, <2 Stage III	Non-High Risk	4 weeks

EXHIBIT 2

[figure not shown]
Exhibit 2. Trial Schema

*Score ≥ 1 Stage IV, ≥ 2 Stage III – high risk on algorithm

EXHIBIT 3

Exhibit 3. Organizational Structure

*Panelists with expertise in machine learning, informatics, palliative care, and cancer care delivery. As per NIH guidance, we do not name panel members in this application so as not to preclude reviewers from their academic institutions.

EXHIBIT 4

Patient Surveys

FEELING HEARD AND UNDERSTOOD

Individuals can respond to each data element using discrete values ranging from 1 (Completely true) to 5 (Not at all true.)

Q1. I felt heard and understood by this provider and team.

- | | | | | |
|--------------------|--------------|-------------------|-----------------------|---------------------|
| 1. Completely true | 2. Very true | 3. Somewhat true. | 4. A little bit true. | 5. Not at all true. |
|--------------------|--------------|-------------------|-----------------------|---------------------|

Q2. I felt this provider and team put my best interests first when making recommendations about my care.

- | | | | | |
|--------------------|--------------|-------------------|-----------------------|---------------------|
| 1. Completely true | 2. Very true | 3. Somewhat true. | 4. A little bit true. | 5. Not at all true. |
|--------------------|--------------|-------------------|-----------------------|---------------------|

Q3. I felt this provider and team saw me as a person, not just someone with a medical problem.

- | | | | | |

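### Acute care use is counted only at participating hospitals while whole practices are randomised, so a chance imbalance in local capture or use can look like an arm difference; add a baseline-adjusted estimate and a coverage list (low severity)

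*Combined protocol and SAP*

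**What the plan says.** Section 6.4 lists among the exploratory outcomes "the impact on acute care utilization including emergency room visits and hospitalizations within participating hospitals in the state of Tennessee", and Section 3.3 sets the same limit: "emergency room visits and hospitalizations within participating hospitals in the state of Tennessee". The hospitals are not named or linked to practices, and no second source, such as claims or patient report, is given for events elsewhere. Section 6.4 follows patients for six months or until death and gives exploratory outcomes descriptive statistics only.

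The practice is the randomised unit. Section 4.1 states: "We will randomize practices into two arms using permuted block randomization to balance practice size, baseline palliative care referral rate". Section 4.4 sets the number: "at up to 17 practices within Tennessee Oncology". Neither hospital coverage nor earlier acute care use is a balancing factor.

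Two further statements bear on where acute care takes place. Section 6.1 describes the study population as similar to other community oncology practices in that "it is not affiliated with a large hospital or health system". Section 8.3, explaining why written consent for the questionnaires is impractical, gives the spread of the network as "over 130 miles between clinics".

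Exhibit 1 already requires a baseline measure of the same kind of event for every scored patient: "Number of ED visits in prior 3 months", with a matching row for inpatient stays, each event scoring 2 points. Its data source is not stated. Section 6.5 mentions mixed-effects models with covariate adjustment but names no covariate.

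**The concern.** Which local hospitals report to the study is a property of the practice, not of the patient. An error in capture therefore does not average out over some 400 patients. It averages out only over the practices, at most about 8 in one arm and 9 in the other. The same holds for real differences in local acute care use that predate the trial.

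An unadjusted summary by arm cannot separate fewer admissions from fewer visible admissions. The plan describes this as assessing an impact, so the two arms will be compared whether or not a p-value is attached. Exhibit 1 holds baseline counts that could show and partly correct an imbalance, but the analysis section gives them no role here.

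**Working it through.** **The plan's own figure.** None is given for acute care use. The only power figure, in Section 6.5, concerns the primary outcome: 180 × 0.9 = 162 evaluable patients per arm, 26.9% v 41.9%, two-sided 0.05, gives 81.4% power against the stated 80%. It reproduces if clustering by practice is ignored, and it has no bearing on this point.

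**Inputs from the documents.** 17 practices at most, so about 8 v 9; practice as the randomised unit; no balancing on coverage or prior use.

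**Inputs assumed, because the documents give none.** Capture by practice, true event rates, equal practice sizes, and no true intervention effect.

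**Step 1: effect on the arm ratio.** With equal true rates, the true rate cancels:

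observed ratio = mean capture in arm 1 ÷ mean capture in arm 0

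SD of log ratio ≈ (SD of capture ÷ mean capture) × √(1/8 + 1/9), and √(1/8 + 1/9) = 0.486.

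- Capture uniform from 60% to 90%: mean 0.75, SD 0.30/√12 = 0.0866. SD of log ratio = 0.1155 × 0.486 = 0.056. The 5-95% range is exp(±1.645 × 0.056), or 0.91 to 1.10. Simulation of 200,000 allocations: 0.912 to 1.097, with 7.5% of allocations off by more than 10%.
- Capture uniform from 40% to 90%: mean 0.65, SD 0.50/√12 = 0.144. SD of log ratio = 0.222 × 0.486 = 0.108. The range is exp(±1.645 × 0.108), or about 0.84 to 1.19. Simulation: 0.836 to 1.195, with 35.6% off by more than 10%.

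**Step 2: the same effect as a risk difference.** Observed difference = true risk × (capture in arm 1 − capture in arm 0). Assume a true six-month risk of 40%.

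- Capture of 80% v 70%: 0.40 × 0.10 = 4 points (ratio 1.14).
- Capture of 80% v 60%: 0.40 × 0.20 = 8 points (ratio 1.33).

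With mean capture of 70%, the SD of the false arm difference is about 0.40 × (between-practice SD of capture) × 0.486:

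| Between-practice SD of capture | By formula | Simulated SD | Simulated 95th percentile of absolute difference |
|---|---|---|---|
| 10 points | 1.9 points | 2.0 points | 3.9 points |
| 20 points | 3.9 points | 3.8 points | 7.4 points |
| 30 points | 5.8 points | 5.9 points | 11.3 points |

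With true risks from 30% to 50%, the 95th percentile runs from 2.8 to 14.3 points over these three SDs.

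**Step 3: how much the baseline counts recover.** This was simulated with counts from the same source as the outcome. Adjustment reduced the SD of the null arm difference in every case, but only by about 3% to 37%, depending on the assumed event rates. A separate simulation looked only at the capture-driven part of the difference. It assumed capture of 40% to 90%, 21 patients per practice, 0.5 to 1.5 events per six months on average, and gamma variation between patients with shape 0.5 to 2. Adjustment removed 9% to 49% of that part, and 27% in the middle case. Neither gain is large, because three-month counts are sparse and a patient's own count is a noisy measure of the practice's capture.

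**The case against.** The case against giving this much weight is substantial, and most of it stands.

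- **Differing capture is not shown.** The documents give no hospital list and no capture rate. The distance between clinics is cited for a consent reason and says nothing about coverage; participating hospitals might serve all practice areas evenly. The lack of a large-hospital affiliation makes uneven capture plausible, no more. The ranges above are assumptions, and the milder one seldom misleads by more than 10%.
- **It is not systematic bias.** A reader might infer that the design tilts this comparison in one direction. It does not: randomisation makes the expected capture difference zero. What remains is chance imbalance in one allocation of few clusters, as with any practice-level factor.
- **The baseline counts are not a cure.** It is tempting to say that they would absorb most of the local difference. Step 3 does not support that. Nor do the documents say that the counts come from the hospitals that supply the outcome; if they do not, adjustment does not correct capture. The counts also help decide who is flagged as high-risk, which complicates their use. A practice random effect makes the interval more honest but does not remove a realised imbalance.
- **The outcome is exploratory.** It has no test, power or hypothesis of its own. Section 3.1 states hypotheses for palliative care visits and aggressive end-of-life utilisation, not for ED visits or admissions, so nothing supports treating this as the trial's headline benefit. The restriction to participating hospitals is also openly stated.
- **Adjustment is arguably covered already.** Section 6.5 leaves room for covariates, but it names none, and Section 6.4 confines exploratory outcomes to descriptive statistics.

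What survives is narrower: descriptive status removes the p-value but not the imbalance, and data already required for the risk score could be used to display it and partly reduce it.

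**Conclusion.** The point holds as a low-severity improvement to an exploratory analysis. As written, the acute care comparison is unadjusted, rests on at most 17 randomised units, and sees only events at participating hospitals. If capture or underlying use differs by practice, a chance imbalance can appear as an arm difference.

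Its size depends wholly on assumptions about capture: a 5-95% range for the ratio of 0.91 to 1.10 at 60-90% capture, and 0.84 to 1.20 at 40-90%, with 8 v 9 practices of equal size and no true effect. Fewer practices or unequal sizes would widen both ranges; more uniform coverage would narrow them.

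The documents do not support concluding that capture does differ between practices or that the result will be biased. The primary outcome, a completed palliative care visit, does not depend on hospital capture, so the primary conclusion is untouched.

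**What to change.** In Section 6.4:

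1. Alongside the descriptive figures, give an estimate for acute care use adjusted for each patient's prior-3-month ED and inpatient counts, with practice as a random effect.
2. State where the Exhibit 1 counts come from, confirm whether that is the same hospital source as the outcome, and show the counts by arm.
3. Before unblinding, list which practices are served by a participating hospital. Keep all practices in the main comparison and report covered practices only as a sensitivity analysis. Making the covered set the main comparison would drop clusters from an already small number, and a yes/no split would still leave partial capture unaddressed.
4. Label the result as use at participating hospitals, not total acute care use.

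The cost is a few sentences of SAP text, a hospital-to-practice list and minor analysis work. The counts are already needed for the risk score; only their source has to be established. The limitation is that adjustment removes only part of any imbalance, and if the sources differ it does not correct capture. The coverage list and the label are then the main safeguards.
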